10 MEASUREMENT OF EFFECT

10.1 Baseline

Imaging assessments will be performed at screening/baseline within 30 days prior to enrollment. Any imaging assessments already completed during the regular workup of the patient within 30 days prior to enrollment, including before signing the main study ICF, may be considered as the baseline images for this study.

The following assessments are required at screening/baseline:

- Chest, abdomen and pelvis CT or magnetic resonance imaging (MRI).
- CT or MRI of other metastatic sites, if clinically indicated. PET scan is an acceptable modality of imaging, as decided by the treating provider.
- Whole-body bone scan per institutional standard of care. Localized bone CT, MRI or X-ray should be performed for any lesions identified on the whole-body bone scan that are not visible on the chest, abdomen and pelvis CT or MRI.
- Brain CT or MRI, if clinically indicated.
- If skin lesions are present at screening, and amenable to photography, color photography should be acquired using a digital camera in clear focus, including a scale/ruler, in such a way that the size of the lesion(s) can be determined from the photograph.
- Measurements of breast mass on imaging are permitted as measurable disease.
- Routine blood tests prior to and during the study are listed in Table 8.

Any potentially measurable lesion that has been previously treated with radiotherapy should be considered as a non-measurable lesion, unless the lesion has clearly progressed since the radiotherapy. Chest X-rays and ultrasound should not be used to measure tumor lesions.

10.2 Response Evaluation

Imaging assessments for response evaluation will be performed every eight weeks (± 7 days) during the first 12 months and every 12 weeks (± 14 days) thereafter. Additional imaging assessments may be performed at any time as clinically indicated. This schedule should be followed until radiological progression is documented, irrespective of compliance to treatment, or until the subject enters follow-up.

Each lesion that is measured at baseline must be measured by the same method and the same local radiologist throughout the study.

10.3 Safety and Tolerability Assessment

Safety assessment will include routine safety monitoring of adverse events and serious adverse events; laboratory testing measurement of vital signs, performance status, physical examination and ECG will be performed at baseline and at each visit thereafter. Laboratory assessments will be performed in the local laboratory.

National Cancer Institute Common Terminology Criteria for Adverse Events (NCI-CTCAE) version 5.0 will be used for all grading. The following safety assessments will be performed along the study:

- Lab parameters: Hematology, biochemistry, coagulation, urinalysis, thyroid
- Adverse events.
- Concomitant medications.
- ECG.
- Medical history, vital signs, performance status, and physical exam.

Table 8 Clinical laboratory parameters collection plan

Test	Items
Hematology	Hematocrit, hemoglobin, MCH, MCHC, MCV, platelets, red blood cells, white blood cells, RBC morphology, differential (basophils, eosinophils, lymphocytes, monocytes, neutrophils)
Chemistry	Calcium, potassium, sodium, glucose, alkaline phosphatase, ALT (SGPT), AST (SGOT), total bilirubin, total protein, albumin, creatinine, chloride, bicarbonate. Direct bilirubin must be performed ONLY if total bilirubin is elevated.
Coagulation at baseline	International normalized ratio (INR), and activated partial thromboplastin time (aPTT) or partial thromboplastin time (PTT).
Urine or serum pregnancy test	At baseline.

All laboratory analysis will be performed locally.

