1.4.1.6 Clinical Experience

Onapristone (ONA) is a type I antiprogestin which prevents the PRA and PRB monomers from dimerizing, inhibits ligand-induced phosphorylation and prevents association of the PR with its coactivators, thus, preventing PR-mediated DNA transcription.(42) In contrast to other antiprogestins, ONA does not allow the PR complex to bind to DNA, minimally modulates PR-mediated genes, and inhibits ligand-induced PR phosphorylation.(33, 34) clinical anticancer activity of ONA has been previously documented in patients with hormone therapy-naïve(43) or tamoxifen-resistant(19) breast cancer (BC).

Onapristone in endocrine sensitive malignancies

More recently, an open-label, multicenter, randomized, parallel-group, phase I study (target n = 60; NCT02052128) included female patients >18 years with PR+ tumors. Fifty-two patients were randomized to five cohorts of extended release (ER) onapristone tablets 10, 20, 30, 40 or 50 mg BID, or immediate release 100 mg QD until progressive disease or intolerance. Primary endpoint was to identify the recommended phase II dose. Secondary endpoints included safety, clinical benefit and pharmacokinetics. Tumor diagnosis included: endometrial carcinoma 12; breast cancer 20; ovarian cancer 13; other 7. Median age was 64 (36–84). No dose-limiting toxicity was observed with reported liver function test elevation related only to liver metastases. The RP2D was 50 mg ER BID. Median therapy duration was eight weeks (range 2–44), and nine patients had clinical benefit lasting at least 24 weeks, including two patients with APRpos endometrial carcinoma.

[figure not shown]
In terms of safety, no dose-limiting toxicity (DLT) was observed. Only transient elevations in LFTs occurred, mostly in patients with liver metastases and abnormal LFTs at baseline. Fifty-one patients discontinued ONA treatment for disease progression, and one for an AE (bilirubin G3 elevation, eventually deemed progression of disease in the liver). Refer to section 8.2 for additional safety information.

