2 HYPOTHESIS AND OBJECTIVES

Table 3 Objectives and Endpoints

Objective	Endpoint
Primary	
Estimate the objective response rate (ORR).	Best overall response of CR or PR, as per RECIST 1.1.
Secondary	
To evaluate progression-free survival rate (PFS).	Time from date of enrollment to the date of first documented disease progression or death due to any cause.
Estimate the disease control rate (DCR).	Best overall response of CR, PR or SD lasting for \geq 24 weeks, as per RECIST 1.1.
To describe time to response and duration of response.	Time to response: Time from enrollment to first documented response (CR or PR). Duration of response: Time between the first date of documented response to progression or death due to breast cancer.
To evaluate the safety and tolerability.	Type, frequency and severity of adverse events and laboratory abnormalities according to CTCAE version 5.0.

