6.2.2 Dose Modification of Onapristone

In the preliminary studies, there were no grade 4 adverse effects (AEs) reported with a single dose of onapristone (10 mg immediate release (IR)) in healthy female volunteers. The treatment doses of onapristone (10–50 mg extended release BID or 00 mg /day) in patients with prostate cancer, breast, ovarian and endometrial cancers also demonstrated no grade 4 toxicities. The majority of the adverse toxicities were related to asthenia (16%), GGT increase (15%), nausea (14%), increased AST (12%), and increased ALT (11%). Two subjects discontinued onapristone due to AEs, and one patients discontinued due to unrelated AEs (cytopenias) due to marrow involvement of the disease secondary to bone metastases. One patient had 25% dose reduction due to liver toxicity, and ultimately discontinued onapristone due to diseases progression and LFT abnormalities. One death was reported within 30 days of discontinuation of onapristone due to

respiratory distress related to progressive lung metastases. Based on this available data under the Context Therapeutics development program, no major adverse effects are anticipated from onapristone, and the table below provides additional guidelines for dose modifications.

Management of severe or intolerable adverse reactions at least possibly, probably or definitely related to onapristone requires dose reduction, temporary interruption, and/or discontinuation of onapristone therapy. A maximum of two dose reductions will be allowed, at which point the patient will be allowed to continue treatment at that reduced dose for the following cycles. Any adverse events even after the dose reductions will indicate treatment discontinuation with onapristone. Dose reduction should be based on the worst preceding toxicity. Please refer to Tables 4, and 5 for guidance.

Table 4 Dose Reduction Steps for Onapristone

Dose level	Dose and schedule	Number of tablets and strength
Starting dose	50 mg BID continuously	2 × 20 mg tablet and 1 × 10 mg tablet
Dose level 1	40 mg BID continuously	2 × 20 mg tablet
Dose level 2	30 mg BID continuously	1 × 20 mg tablet and 1 × 10 mg tablet

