7.5.2 Onapristone Identified Safety Risk

In the phase I trial [Cottu 2018], seven patients (13%) experienced transient dose interruptions for AEs (one each: nausea, ALT increase, gastroenteritis, GGT increased, thoracic pain, postprocedural cellulitis, LDH increase, abdominal pain and atrial fibrillation).

Thirty patients (58%) experienced at least one grade 3 or grade 4 adverse event. In 10 patients (19%), the following adverse events were considered related to ONA: increased GGT (13%), increased AST and ALP (6% each), increased bilirubin (4%), and increased ALT and LFTs, asthenia and pulmonary embolism (2% each). All except two of these AEs were associated with progressive disease: one G3 GGT elevation at week 12 in a responding patient, lasting one month with associated transient G1 AST and bilirubin increase, with no clinical symptoms; and the other a G3 GGT elevation at week 3, lasting three weeks, in a patient with liver metastases and baseline G1 GGT elevation. Both elevations decreased spontaneously with no action taken. None of the G3 AST, ALT or bilirubin elevations were considered to be dose limiting by the independent data review committee due to the presence of concurrent progressive disease in the liver.

7.5.3 ^{18}F -FFNP PET/CT Identified Safety Risk

To date, no significant adverse events have been reported as a result of the intravenous administration of ^{18}F -FFNP for PET imaging applications [54].

As with any IV administered agent, ^{18}F -FFNP could cause an allergic reaction that could potentially pose a threat to life (anaphylaxis). This has not been observed in reported human exposure to date. Reasonable precautions should be taken, consistent with normal radiologic and clinical facility practice. The patient should be monitored until the PET procedure is completed, and trained personnel and emergency equipment should be available per facility standards.

For purposes of informed consent regarding reasonably foreseeable risks to subjects in trials utilizing ^{18}F -FFNP, the following potential adverse events are considered:

- Injection-related risks that may include infection, or accidental extravasation of the dose that may lead to discomfort, localized pain, or infection (rare occurrence).
- Risks related to allergic reaction/anaphylaxis that may be life-threatening (extremely rare occurrence).

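### The scheduled chemistry panel omits GGT, the onapristone laboratory abnormality with the highest reported rate, so the safety endpoint does not measure it systematically

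*Combined protocol and SAP*

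**What the plan says.** **Endpoint.** Section 2 (Table 3) defines the safety endpoint as "Type, frequency and severity of adverse events and laboratory abnormalities according to CTCAE version 5.0".

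**Panel.** Section 10.1 refers to Table 8 for the routine bloods before and during the study. The chemistry row of Table 8 (section 10.3) is "Calcium, potassium, sodium, glucose, alkaline phosphatase, ALT (SGPT), AST (SGOT), total bilirubin, total protein, albumin, creatinine, chloride, bicarbonate", with direct bilirubin added only when total bilirubin is raised. GGT is not listed. The Study Calendar schedules blood chemistry with liver function tests at screening, cycle 1 day 1, day 1 of each later cycle, end of treatment and the safety visit, but names no analytes. Where Table 5 (section 6.2.2) uses the term liver function tests, it specifies ALT or AST.

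**Prior data.** Section 1.4.1.6 gives the phase I size: "Fifty-two patients were randomized to five cohorts". Section 7.5.2 reports "Thirty patients (58%) experienced at least one grade 3 or grade 4 adverse event" and then "In 10 patients (19%), the following adverse events were considered related to ONA". The list that follows begins "increased GGT (13%), increased AST and ALP (6% each), increased bilirubin (4"%) and puts ALT at 2%. Section 6.2.2, on the wider development programme, gives "GGT increase (15"%), beside AST 12% and ALT 11%. On attribution, section 7.5.2 says "All except two of these AEs were associated with progressive disease: one G3 GGT elevation at week 12 in a responding patient". The other exception was also a grade 3 GGT rise, at week 3, in a patient with liver metastases and a grade 1 elevation at baseline.

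**The concern.** A laboratory abnormality is counted only if the analyte is measured. The protocol names GGT as the leading laboratory finding for onapristone in its risk text, but schedules every other commonly reported liver test and leaves this one out. Ordinary adverse event reporting is a poor substitute. Of the two GGT rises not tied to progression, the week 12 event had no symptoms, and both resolved without intervention, so events of this kind come to light mainly when someone orders the test.

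At stake is the interpretability of one part of a secondary endpoint. Some sites may run GGT in a local panel and others may not. A final table would then mix subjects tested from baseline, subjects tested once for cause and subjects never tested. The resulting percentage could not be set against the phase I figure, and in a single-arm trial of a combination the phase I data are the natural reference for what onapristone contributes.

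**Working it through.** **1. Reproduce the phase I percentages (n = 52).**
- Any grade 3-4 event: 30/52 = 57.7%, printed 58%.
- Related events: 10/52 = 19.2%, printed 19%.
- Related GGT: the count is not printed. 7/52 = 13.5% rounds to 13%, whereas 6/52 = 11.5% and 8/52 = 15.4% do not, so 7 is the only count that fits.
- AST and ALP: 3/52 = 5.8% each, printed 6%. Bilirubin: 2/52 = 3.8%, printed 4%. ALT: 1/52 = 1.9%, printed 2%.

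The printed figures are consistent with one denominator of 52.

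**2. Precision of the ranking.** Exact (Clopper-Pearson) 95% intervals are 5.6% to 25.8% for GGT (7/52) and 1.2% to 15.9% for AST or ALP (3/52). They overlap. The statement that GGT is most frequent therefore concerns reported point estimates. On the programme-wide figures the lead is narrow: 15% against 12% and 11%.

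**3. Expected yield among 39 subjects.**

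| Rate assumed | Source | Expected = 39 × rate | P(at least one) = 1 − (1 − rate)^39 |
|---|---|---|---|
| 13% | related grade 3-4, section 7.5.2 | 5.1 | 99.6% |
| 15% | all reported, section 6.2.2 | 5.9 | 99.8% |
| 2/52 = 3.8% | related and not tied to progression | 1.5 | 1 − (50/52)^39 = 78% |

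Of about 7 related GGT events in phase I, 7 − 2 = 5 accompanied progression. The first and third rows bracket what a scheduled test might find: about 5 subjects if every related event is counted, about 1.5 if only those not coinciding with progression are counted.

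**4. What measurement would give.** If 5 of 39 tested subjects had an event, the exact 95% interval would be 4.3% to 27.4%: wide, but a rate with a known denominator. As written, no subject is required to have a GGT value, so the number tested is undefined and no interval can be attached.

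**5. Do the scheduled visits fall at useful times?** Cycles last 28 days, so cycle 2 day 1 is study day 29 and cycle 4 day 1 is day 1 + 3 × 28 = 85. A rise starting in week 3 (days 15 to 21) and lasting three weeks covers day 29. A rise starting in week 12 (days 78 to 84) and lasting a month covers day 85. Chemistry blood is already due at both visits.

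**The case against.** The strongest objection concerns the cost of the remedy. Table 5 has no GGT row, so a related rise would come under its row for other non-hematological toxicity, where grade 3 leads to interruption of onapristone and grade 4 to discontinuation. In phase I the two rises not tied to progression resolved with no action. Scheduling GGT could thus trigger dose changes for an isolated enzyme rise, and any discontinuation could count toward the safety boundaries in section 9.2 (more than 3 of 11, 4 of 21, 5 of 30 or 7 of 39). This stands, and it must be disclosed with the proposal.

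Other objections also stand in part. ALP, ALT, AST and bilirubin are all scheduled, so hepatic monitoring in general is not missing. The week 12 GGT event came with grade 1 rises in AST and bilirubin, both on the panel, so it would have left some trace. No rule or planned analysis names GGT, and adverse events receive only descriptive tables.

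Some stronger readings are tempting but not supported:
- A reader might infer that the trial cannot detect GGT rises at all. Laboratories are local, and section 7.2.1 has adverse events recorded, so a value obtained locally can be captured. What is missing is systematic measurement.
- A reader might call GGT the most sensitive hepatic marker. The documents give frequencies, not sensitivity for liver injury.
- A reader might fear that an interaction with fulvestrant would go unseen. The enzymes that section 7.5.1 reports for fulvestrant are ALT, AST and ALP, all scheduled, and section 7.5.5 considers an interaction unlikely.
- A reader might predict a reported rate near zero. That depends on local practice, which the documents do not describe.

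**Conclusion.** The point holds as a gap between the stated endpoint, the protocol's own risk data and the collection plan. GGT is not systematically measured, although it has the highest reported rate of any onapristone laboratory abnormality. The size is about 5 of 39 subjects with a related grade 3-4 rise at the phase I rate, falling to about 1.5 of 39 if only events not accompanied by progression are counted.

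This rests on four assumptions: the 13% refers to grade 3-4 events, as its position in section 7.5.2 implies; the GGT count is 7, inferred from the percentage; phase I rates from several tumour types carry over to this population and to the combination; and Table 8 is the complete routine panel, as section 10.1 indicates. The primary response analysis and the two-stage design are untouched. This is an inexpensive improvement to a descriptive secondary endpoint, not a defect that undermines the trial.

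**What to change.** Add GGT to the chemistry row of Table 8 at screening and at each chemistry time point already in the Study Calendar. Tabulate it by CTCAE v5.0 grade with the other liver tests, showing the number of subjects tested and the baseline grade. Flag whether each rise coincided with progression, so that both counts above can be reported. If the sponsor prefers not to collect GGT, the plan should say why and state that GGT was not systematically measured.

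Costs: one more analyte on blood already drawn, with no new visit; a less favourable laboratory toxicity table; and the Table 5 and section 9.2 consequences described above. Before the change takes effect the sponsor should reconcile Table 5, section 7.5.2 and Table 8 on how GGT rises are handled, and state whether a resulting discontinuation of onapristone counts toward the section 9.2 boundaries. No clinical rule is proposed here.

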10.4 Other Assessments

Cardiac Assessments

A standard 12-lead ECG will be performed at screening. The interpretation of the ECG must be made by a qualified physician and documented in the ECG section of the CRF. Clinically significant abnormalities present when the patient signed informed consent should be reported on the medical history CRF page. New or worsened clinically significant findings occurring after informed consent must be recorded on the adverse events CRF page. Additional cardiac imaging during treatment is to be performed as clinically indicated.

10.5 Tumor Biopsy and Plasma Analyses

A summary of biomarker assessments and biomarker sample collection plan is in Tables 9, 10 and 11. All assessments will be performed by a central designated laboratory.

There are no plans to share the results with subjects. The correlative studies are not expected to provide adequate information to guide any future treatment decisions.

All FFPE tumor blocks, unstained histological slides, and research blood samples need to be shipped to:

Attn: [name]
 [name] lab
 [name]
 Wisconsin Diagnostic Laboratories Building
 [name]
 [name]

Sample Processing: Upon receipt of the samples, MCW's lab manager, [name], will be in charge of tissue sample processing, distribution, and shipment of the samples for

biomarker analysis by [name] (MCW) and Natera Inc. (**[name]**, Tissue Bank Manager, Medical College of Wisconsin, Department of Pathology, [contact], Office [contact], Lab [contact], [contact], MCW Tissue Bank Website: www.mcw.edu/tissuebank)

If adequate tissue is not available for all the evaluations of study biomarkers, additional biopsies may be requested. However, if a subject chooses to decline additional biopsies, he or she would still be eligible for study enrollment. Any remaining tissue of the tumor samples will be preserved as coded specimens in the MCW Tissue Bank provided the subject has provided consent for the tissue banking. Subjects who decline to participate in tissue banking will remain eligible for the proposed study. FFPE blocks are stored long-term in metal Sakura block cabinets under ambient temperature. Room temperature is recorded and monitored daily. Samples are logged and tracked in the MCW Tissue Bank's tissue tracking software, OnCore®.

10.5.1 Tissue Analysis

An FFPE tumor biopsy block or up to 20 superplus frost slides, with unstained histological sections at 5 micrometer thickness are required at the time of study entry. A single H&E slide is also requested.

If the archival tissue has not been obtained in the 18 months prior to study registration, analysis of a more recent biopsy will be required for study entry if deemed safe (minimal risk to patient) by the treating physician. ER/PR/HER2 testing will be performed at the facilities/clinics where the patients are routinely seen, and the biopsy was performed. The remaining block will be sent (for sectioning or 20 precut sections) to [name] at the above-mentioned address.

- 1. Tissue analysis for IHC, protein expression and other makers (performed by [name], MD, PhD):** Protein expression will be quantified on slides, using optimized immunohistochemistry [IHC] protocols for planned study biomarkers. Ki-67 assessment on pre- and post-treatment specimens would include assessment by manual counting of stained tumor cells by our pathologists, as well as quantitative IHC.
- 2. The degree of PgR expression levels will be determined using standard immunohistochemistry methodology on all tissue and reported as percent tumor cells with PgR staining. In cases where no PgR results are available, one to three 4-micrometer histological sections on superplus frost slides will be used for IHC testing. This testing will be performed at the Medical College of Wisconsin CLIA-approved clinical pathology laboratory using the Dako progesterone receptor antibody. Upon receipt of the slide in the clinical laboratory, results will be reported within 72 hours. The relationship between tumor response and degree of PgR expression, and/or PgR signaling, will be examined.**
- 3. Additional exploratory biomarkers will be evaluated on FFPE tissue, including phosphorylated PgR and PgR target gene expression. If $\geq 1\%$ phosphorylated Ser294 PgR (pPgR) tumor staining is seen on ≥ 1 slide the tumor will be considered to be pPgR+. Nuclear localization of pPgR will also be evaluated. PgR target gene analysis will be completed using the NanoString nCounter oncology panel system. NanoString analysis will require 25 ng of FFPE tissue. Tables 9, 10 and 11 include a complete list of tissue and blood-based genomic alterations of the breast tumor samples, and their preparation for this study.** 
- 4. Tissue analysis for ctDNA testing (performed by Natera):** Tumor samples will be

processed and shipped to Natera for ctDNA testing as noted above.

Table 9		
Biomarker Correlatives	Tissue Biopsy	Liquid Biopsy (Plasma)
Collection	Pre-treatment core biopsy (archival or new FFPE biopsy) and post-treatment core biopsy (FFPE; if available)	Three time points: pre, during (C3D1) and post-treatment (or at next follow-up visit)
Immunohistochemistry (IHC)	ER, PgR, HER2, Ki67, CD24, CD44, LDH1, KLF4, CK 5/6, Phospho-Ser294-PgR	
Mutational Analysis of the tumor tissue (performed by Natera)	A personalized assay is designed based on the unique mutation signature of each patient's tumor	A personalized assay is designed based on the unique mutation signature of each patient's tumor and correlated with peripheral blood. This will allow to accurately monitor for the presence or absence of the disease over time.

